5.3.6 Clinical Studies

Everolimus has been investigated in various indications, including solid organ transplantation, hematologic and non-hematologic malignancies, and rheumatoid arthritis. Efforts to evaluate everolimus in the setting of rheumatoid arthritis have since been discontinued. Everolimus has been in clinical development for solid organ transplantation since 1996 and obtained marketing authorization in 2003 under the trade name Certican®. Certican® is indicated for prophylaxis of rejection in renal and cardiac transplantation in over 60 countries, including the majority of the European Union. Certican® is commercially available in tablets strengths of .25, .5, .75 and 1 mg. In the United States Certican® is an investigational new drug in development for the indication of transplantation. Everolimus has been in development for patients with various

hematologic and nonhematologic malignancies since 2002, and has been evaluated either as a single agent or in combination with other antitumor agents, tyrosine kinase inhibitors, antibodies and aromatase inhibitors. Patients with metastatic renal cell carcinoma (mRCC) who failed a previous vascular endothelial growth factor receptor (VEGFr) tyrosine kinase inhibitor (TKI), advanced breast cancer patients, carcinoid neuroendocrine tumors, pancreatic islet cell tumors (pNET), hematologic malignancies including chronic myelogenous leukemia (CML) non-Hodgkin's and mantle cell lymphoma, hepatocellular, gastric, colorectal, gastrointestinal stromal tumors (GIST), prostate and other indications including sarcoma, head, neck, lung and glioblastoma multiforme conducted in investigator sponsored studies have or are being conducted. A Phase III, randomized, double blind, placebo controlled study in patients with mRCC who progressed on a VEGFr TKI recently demonstrated that everolimus, administered daily at an oral dose of 10 mg administered provides positive clinical benefit.¹⁰ Median progression free survival (PFS) was prolonged from 1.87 months for patients receiving placebo to 4.01 months for everolimus treated patients, assessed by central independent review blinded to clinical data (hazard ratio 0.30, 95% CI 0.22-0.40, $p < 0.0001$). Median PFS was prolonged from 1.87 months for patients receiving placebo to 4.9 months for everolimus treated patients, assessed by central independent review blinded to clinical data (hazard ratio 0.33, 95% CI 0.25-0.43, $p < 0.001$). Additionally, two Phase III combination studies are ongoing for patients with advanced pNET receiving best supportive care, and one in carcinoid tumors with Sandostatin LAR® Depot.

An international, multicenter, randomized, double-blind trial comparing AFINITOR 10 mg daily and placebo, both in conjunction with best supportive care, was conducted in patients with metastatic renal cell carcinoma whose disease had progressed despite prior treatment with sunitinib, sorafenib, or both sequentially. Prior therapy with bevacizumab, interleukin 2, or interferon- α was also permitted. Randomization was stratified according to prognostic score1 and prior anticancer therapy.

Progression-free survival (PFS), documented using RECIST (Response Evaluation Criteria in Solid Tumors) was assessed via a blinded, independent, central radiologic review. After documented radiological progression, patients could be unblinded by the investigator: those randomized to placebo were then able to receive open-label AFINITOR 10 mg daily. In total, 416 patients were randomized 2:1 to receive AFINITOR (n=277) or placebo (n=139). Demographics were well balanced between the two arms (median age 61 years; 77% male, 88%

Caucasian, 74% received prior sunitinib or sorafenib, and 26% received both sequentially). AFINITOR was superior to placebo for progression-free survival. The treatment effect was similar across prognostic scores and prior sorafenib and/or sunitinib. The overall survival (OS) results were not mature and 32% of patients had died by the time of cut-off.

Supplier(s)

Novartis Pharmaceuticals Corporation will supply everolimus (Afinitor^R) to study participants at no charge.

Drug Handling

Procedures for proper handling and disposal of anticancer drugs should be considered. AFINITOR tablets should not be crushed. Direct contact of crushed tablets with the skin or mucous membranes should be avoided. If such contact occurs, wash thoroughly as outlined in the references. Personnel should avoid exposure to crushed tablets.

Dosage form

Everolimus will be supplied as tablets for oral administration.

Packaging

Everolimus will be provided to patients through the Investigational Drug Supply Pharmacy at the Winship Cancer Institute at the beginning of each cycle. Blister packets will contain sufficient number of capsules for one cycle of dosing.

Storage

Store AFINITOR (everolimus) tablets at 25° C (77°F); excursions permitted between 15°–30°C (59°–86°F). Store in the original container, protect from light and moisture. Keep this and all drugs out of the reach of children.

5.4 Screening and Eligibility

The Investigator is responsible for keeping a record of all subjects who sign an Informed Consent Form for entry into the study. All subjects will be screened for eligibility. Screening procedures are outlined in Section 2, Schedule of Study Assessments and unless otherwise specified, must take place within 28 days prior to initiation of therapy.

Approximately 45 subjects with advanced refractory solid malignancies will be screened for enrollment and must meet the eligibility criteria below.

Subjects must meet the following inclusion/exclusion criteria to be eligible for the study.

5.4.1 Inclusion Criteria

- Subjects must meet the following inclusion/exclusion criteria to be eligible for the study.
- Ability to understand and willingness to voluntarily sign an informed consent form.
- Histologic or cytologic confirmation of a solid malignancy
- Age ≥ 18 years at the time of signing the informed consent form. Because no dosing or adverse event data are currently available on the use of everolimus in combination with lenalidomide in patients < 18 years of age, children are excluded from this study.
- Able to adhere to the study visit schedule and other protocol requirements.
- Patients must have at least one measurable site of disease according to RECIST 1.1 criteria that has not been previously irradiated. If the patient has had previous radiation to the marker lesion(s), there must be evidence of progression since the radiation.
- Diagnosed with advanced refractory solid malignancies or intolerant of standard therapy for the stage of the disease (because there is currently no standard approved therapy for adenoidcystic carcinoma, therefore there is no requirement of prior therapy for this patient population).
- All previous cancer therapy, including radiation, hormonal therapy and surgery, must have been discontinued at least 4 weeks prior to treatment in this study. A minimum of 6 weeks treatment break is required in case of nitrosoureas or mitomycin C.
- ECOG performance status of 0 - 2 at study entry (see Appendix A).
- Able to receive prophylactic anticoagulation with aspirin, warfarin or low molecular weight heparin when required for lenalidomide administration
- Fasting serum cholesterol ≤ 300 mg/dL OR ≤ 7.75 mmol/L AND fasting triglycerides $\leq 2.5 \times$ ULN. NOTE: In case one or both of these thresholds are exceeded, the patient can only be included after initiation of appropriate lipid lowering medication.
- Laboratory test results within these ranges:
 - Absolute neutrophil count $1500 \geq /\text{mm}^3$
 - Platelet count $\geq 100,000/\text{mm}^3$
 - Hb ≥ 9 g/dL
 - Creatinine within institutional limits of normal or Creatinine clearance ≥ 60 ml/min/m² if elevated creatinine (see Appendix F: Cockcroft-Gault estimation of CrCl):

-
- Total bilirubin < 2.0 mg/dL or < 1.5.0 x ULN for the institution whichever is higher
 - AST (SGOT) and ALT (SGPT) < 2.x ULN or < 5 x ULN if hepatic metastases are present.
 - All study participants must be registered into the mandatory Revlimid REMS® program, and be willing and able to comply with the requirements of the REMS® program.
 - Females of reproductive potential must adhere to the scheduled pregnancy testing as required in the Revlimid REMS® program.
 - Females of childbearing potential (FCBP)[†] must have a negative serum or urine pregnancy test with a sensitivity of at least 50 mIU/mL within 10 – 14 days prior to and again within 24 hours of prescribing lenalidomide (prescriptions must be filled within 7 days) and must either commit to continued abstinence from heterosexual intercourse or begin TWO acceptable methods of birth control, one highly effective method and one additional effective method AT THE SAME TIME, at least 28 days before she starts taking lenalidomide. FCBP must also agree to ongoing pregnancy testing. Men must agree to use a latex condom during sexual contact with a FCBP even if they have had a successful vasectomy. See Appendix B: Risks of Fetal Exposure, Pregnancy Testing Guidelines and Acceptable Birth Control Methods.

5.4.2 Exclusion criteria

- Uncontrolled intercurrent illness including, but not limited to, ongoing or active infection, symptomatic congestive heart failure, unstable angina pectoris, cardiac arrhythmia, or psychiatric illness/social situations that would limit compliance with study requirements including signing the informed consent form.
- Pregnant or breast feeding females. (Lactating females must agree not to breast feed while taking lenalidomide).

[†] A female of childbearing potential is a sexually mature woman who: 1) has not undergone a hysterectomy or bilateral oophorectomy; or 2) has not been naturally postmenopausal for at least 24 consecutive months (i.e., has had menses at any time in the preceding 24 consecutive months).

-
- Any condition, including the presence of laboratory abnormalities, which places the subject at unacceptable risk if he/she were to participate in the study or confounds the ability to interpret data from the study.
 - Use of any other experimental drug or therapy within 28 days of baseline.
 - Known hypersensitivity to thalidomide or everolimus (including other rapamycins, sirolimus and temsirolimus).
 - The development of erythema nodosum if characterized by a desquamating rash while taking thalidomide or similar drugs.
 - Prior treatment with lenalidomide or everolimus
 - Concurrent use of other anti-cancer agents or treatments.
 - Patients known to be positive for HIV or infectious hepatitis, type B or C requiring active therapy (hepatitis B seropositivity due to Hep B virus vaccine is not an exclusion). Patients on combination antiviral therapy are ineligible because of the potential for pharmacokinetic interactions with everolimus and or lenalidomide. In addition, these patients are at increased risk of lethal infections when treated with marrow-suppressive therapy. Appropriate studies will be undertaken in this patient population.
 - Liver disease such as cirrhosis or severe hepatic impairment (Child-Pugh class C).
 - History of liver disease, such as cirrhosis or chronic active hepatitis B and C.
 - Presence of Hepatitis B surface antigen (HbsAg)
 - Presence of Hepatitis C antibody test (anti-HCV)
 - Note: A detailed assessment of Hepatitis B/C medical history and risk factors must be done at screening for all patients. HBV DNA and HCV RNA PCR testing are required at screening for all patients with a positive medical history based on risk factors and/or confirmation of prior HBV/HCV infection.
 - Symptomatic brain metastasis. Patients with treated brain metastasis must be completely weaned off of steroid therapy for at least 14 days prior to starting protocol therapy
 - Patients receiving chronic, systemic treatment with corticosteroids or another immunosuppressive agent. (Topical or inhaled corticosteroids are allowed).
 - Patients should not receive immunization with attenuated live vaccines within one week of study entry or during study period

-
- Diagnosed venous thromboembolic disease within the preceding 6 months (patient on full dose or prophylactic anticoagulation are eligible)
 - Patients receiving any medications or substances that are inhibitors or inducers of CYP450 enzyme(s) are ineligible. Lists of excluded medications and substances known or with the potential to interact with the CYP450 enzyme(s) are provided in Appendix E.
 - History of other malignancies except: (i) adequately treated basal or squamous cell carcinoma of the skin; (ii) curatively treated, a) in situ carcinoma of the uterine cervix, b) prostate cancer, or c) superficial bladder cancer; or (iii) other curatively treated solid tumor with no evidence of disease for ≥ 3 years
 - Patients, who have had a major surgery or significant traumatic injury within 4 weeks of start of study drug, patients who have not recovered from the side effects of any major surgery (defined as requiring general anesthesia) or patients that may require major surgery during the course of the study
 - Patients with an active, bleeding diathesis

5.4.3 Inclusion of Women and Patients of Ethnic Minority Background

Both men and women of all races and ethnic groups are eligible for this trial.

5.5 Visit schedule and assessments

Screening Assessments and all on study scheduled visits and assessments are outlined in Section 2 Table of Study Assessments.

At treatment discontinuation, subjects will undergo off study evaluations per the Schedule of Assessments, Section 2. In addition, a safety assessment will be done approximately 30 days post the last dose of protocol therapy.

5.6 Drug Administration

5.6.1 Treatment assignments

Patient will be assigned to dose cohort in the order they enter the study using the modified Fibonacci dose escalation schema as detailed in Table 1, section 5.1.

5.6.2 Dosing regimen

The planned starting dose of lenalidomide for investigation is 10 mg/day, orally on days 1 - 28 (28 day cycle). Dosing will be in the morning at approximately the same time each day. Prescriptions must be filled within 7 days. Subjects deemed by the Principal Investigator to be at heightened risk of venous thromboembolism will receive prophylaxis with daily aspirin (81mg or 325 mg) or low molecular weight heparin if intolerant to ASA. Coumadin should be used with caution and close monitoring of INR required.

If a dose of lenalidomide is missed, it should be taken as soon as possible on the same day. If it is missed for the entire day, it should not be made up. Patients who take more than the prescribed dose of lenalidomide should be instructed to seek emergency medical care if needed and contact study staff immediately.

The planned starting dose of everolimus (RAD001) is an approved dose of 5 mg/day on a continuous basis, days 1- 28. RAD001 will be self-administered (by the patients themselves). The investigator will instruct the patient to take the study drug exactly as specified in the protocol. RAD001 will be administered orally as once daily dose of 5 mg or 10 mg (one or two 5 mg tablets) starting from study day 2, cycle 1 until progression of disease or unacceptable toxicity. Patients will be instructed to take RAD001 in the morning, at the same time each day.

RAD001 may be taken with or without food.

If vomiting occurs, no attempt should be made to replace the vomited dose.

All dosages prescribed and dispensed to the patient and all dose changes during the study must be recorded.

Medication labels will comply with US legal requirements and be printed in English. They will supply no information about the patient. The storage conditions for study drug will be described on the medication label.

RAD001 will be provided by Novartis. RAD001 is formulated as tablets for oral administration of 5mg strength. Tablets are blister-packed under aluminum foil in units of 10 tablets, which should be opened only at the time of administration as drug is both hygroscopic and light-sensitive.

Subjects experiencing adverse events may need study treatment modifications (See section 5.7).

5.6.3 Special Handling Instructions

Females of childbearing potential should not handle or administer lenalidomide or everolimus unless they are wearing gloves.

5.6.4 Record of administration

Accurate records will be kept in the source documents of all drug administration (including prescribing and dosing).

5.7 Dose Continuation, Modification and Interruption

Subjects will be evaluated for adverse events (AEs) at each visit with the NCI CTCAE v4.0 (Appendix C: NCI CTCAE v4.0) used as a guide for the grading of severity. Sections below describe dose reduction steps, instructions for initiation of a new cycle of therapy and dose modifications during a cycle of therapy.

5.7.1 Dose Reduction Steps

This dose reduction steps will guide dose modification for Lenalidomide and Everolimus in patients who either experienced a DLT or who develop treatment related toxicity beyond cycle 1 of therapy. The decision for dose escalation or deescalation for dose cohorts will however proceed according to the dose escalation schema (Table 1, Section 5.1).

Table 3: LENALIDOMIDE Dose Reduction Steps

If toxicity occurred at

Reduce dose to

25 mg	20 mg daily
20 mg	15 mg daily
15 mg	10 mg daily
10 mg	10 mg daily on Days 1-21 every 28 days
10 mg daily on Days 1 – 21 of 28	5 mg daily on Days 1-21 every 28 days

Table 4: Everolimus Dose Reduction Steps

If the Toxicity occurred at --- (MG/DOSE):	Reduce dose to --- (MG/DOSE):
0 (starting dose)	10 mg daily
-1	5 mg daily
-2	5 mg every other day

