This is a phase I, open-label, single institution, non-randomized study of escalating doses of daily, orally administered lenalidomide in combination with standard doses of everolimus, an orally available mTOR inhibitor. The trial is open to patients with advanced solid malignancies who have failed or are intolerant of available standard treatment options for their disease. Dose escalation will proceed in a modified Fibonacci 3+3 fashion with the requirement that dose escalation to the next level can only proceed if 0 of 3 or ≤ 1 of 6 patients experience a dose limiting toxicity (DLT). Five escalating dose cohorts and three deescalating dose cohorts (if DLT is encountered with the starting dose) will be used to evaluate different doses of lenalidomide and everolimus starting with the approved and or clinically relevant doses of both agents. The proposed starting dose level 1 is 10mg of lenalidomide in combination with 5mg of everolimus both administered on a once daily continuous dosing schedule for 28 days respectively in a 28-day cycle. A serial de-escalation to 10mg of lenalidomide (21 of 28 days) and 5mg of everolimus every other day will be carried out if DLT is observed in $\geq 33\%$ of patients enrolled to the starting dose cohort. The MTD is the highest dose level of lenalidomide and everolimus (up to a maximum dose of 25mg and 10mg respectively) at which $<33\%$ of the dose cohort experiences DLT after 1 cycle (28 days) of therapy. The established MTD will be the recommended dose for follow-up phase II study. To obtain preliminary evidence of potential clinical benefit of this combination, an expanded cohort of 15 patients with clear cell renal cell carcinoma, adenoidcystic carcinoma and neuroendocrine tumors will be treated at the defined MTD.

A parallel expansion cohort of 9 patients with adenoidcystic cancer will be treated at the RP2D

STUDY ENDPOINTS**Primary:**

- The MTD is the maximum doses of both drugs that can be administered without inducing DLT in $\geq 33\%$ of the treated patient cohort.
- Safety will be assessed according to NCI CTCAE 4.0v
- Assessment of DLT will be performed during the first cycle only and the following will constitute DLT in this study:
 - Grade 4 hematological toxicity lasting more than 7 days
 - Grade 4 Neutropenia of any duration in the presence of fever ≥ 38.5 c
 - Grade ≥ 3 nausea and or vomiting in spite of standard supportive therapy
 - Grade ≥ 3 non-hematologic toxicity (excluding alopecia)

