5.1 Overall design

This is a phase I, open-label, single institution, non-randomized study of escalating doses of daily, orally administered lenalidomide in combination with standard doses of everolimus, an orally available mTOR inhibitor. The trial is open to patients with advanced solid malignancies who have failed or are intolerant of available standard treatment options for their disease. Dose escalation will proceed in a modified Fibonacci 3+3 fashion with the requirement that dose escalation to the next level can only proceed if 0 of 3 or ≤ 1 of 6 patients experience a dose limiting toxicity (DLT). Four escalating dose cohorts and three deescalating dose cohorts will be used to evaluate different doses of lenalidomide and everolimus starting with the approved and or clinically relevant doses of both agents. The proposed starting dose level 1 is 10mg of lenalidomide (days 1 – 28) in combination with 10mg of everolimus (days 1 - 28) in a 28-day cycle. A serial de-escalation to 10mg of lenalidomide (days 1-21 of a 28 day cycle) and 5mg of everolimus will be carried out if DLT is observed in $\geq 33\%$ of patients enrolled to the starting dose cohort. The MTD is the highest dose level of lenalidomide and everolimus (up to a maximum dose of 25mg and 10mg respectively) at which $<33\%$ of the dose cohort experiences DLT after 1 cycle (28 days) of therapy. The established MTD will be the recommended dose for follow-up phase II study. To obtain preliminary clinical benefit of this combination, an expanded cohort of 15 patients with clear cell renal cell carcinoma, adenoidcystic carcinoma and neuroendocrine tumors will be treated at the define MTD. To allow for assessment of drug-drug interaction using PK analysis, lenalidomide will be administered alone on day 1 of the first cycle followed by both agents on day 2 cycle 1. Both drugs will be started simultaneously on day 1 of all subsequent cycles.

In addition, a parallel cohort of 9 additional patients with adenoicystic cancer will be treated at the RP2D. This is to enable us to obtain further evidence in support of the efficacy of this regimen in patients with adenoicystic cancer as observed in the limited number of patients with this cancer type who were enrolled in the escalation phase of the study.

Table 1

Dose Level	Lenalidomide (day 1 to 28)	Everolimus (day 1-28)	Patient Enrolment	Remarks
-2	10mg Days 1-21	5mg every other day	3 + 3	If DLT, study will close without defining a MTD

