-1	10mg Days 1-21	5mg	3 + 3	Deescalate to level -2 if ≥ 1 of 6 patients experience DLT, otherwise declare as MTD and expand the cohort
Starting Dose 1	10mg	5mg	3 + 3	Escalate to level 2 if 0 of 3 or 1 of 6 patients experience DLT, otherwise deescalate 1 level
2	15mg	5mg	3 + 3	Escalate to level 3 if 0 of 3 or 1 of 6 patients experience DLT, otherwise deescalate 1 level
3	20mg	5mg	3 + 3	Escalate to level 4 if 0 of 3 or 1 of 6 patients experience DLT, otherwise deescalate 1 level
4	25mg	5mg	3 + 3	if ≥ 1 of 6 patients experience deescalate 1 level, otherwise declare as MTD
5	25mg	10	3 + 3	if ≥ 1 of 6 patients experience deescalate 1 level, otherwise declare as MTD
MTD	TBD	TBD	15	Expanded cohort of 15 patients restricted to patients with renal cell carcinoma, adenoicystic carcinoma and neuroendocrine tumors

5.1.1 Blood Sample Collection:

Blood samples will be collected in heparinized green top tubes (3 mls for PK samples and 7 mls for PBMC collection), red top tube (7 mls to obtain serum sample for cytokine assay). PBMC will be purified using standard Ficoll-Paque gradient centrifugation according to the instructions of the manufacturer (Amersham Pharmacia, Uppsala, Sweden). All samples must be stored away within 1 hour of collection by refrigeration at -80°C until ready for assay.

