5.7.2 Instructions for initiation of a New Cycle

A new course of treatment may begin on the scheduled Day 1 of a new cycle if::

- The ANC is $\geq 1500/\text{mm}^3$;
- The platelet count is $100,000 \geq /\text{mm}^3$; (If held during the previous cycle for low platelet count, prophylactic anti-coagulation should be re-started when platelet count is $\geq 75,000$)
- Any drug-related rash or neuropathy that may have occurred has resolved to \leq grade 1 severity;
- Any other drug-related adverse events that may have occurred have resolved to \leq grade 2 severity.

If these conditions are not met on Day 1 of a new cycle, the subject will be evaluated weekly and a new cycle of treatment will not be initiated until the toxicity has resolved as described above. If a lenalidomide or everolimus dose reduction was taken during the previous cycle, and the cycle was completed without requiring further dose modification, then the next cycle will start at the same reduced dose. **If drug dosing was omitted for the remainder of the previous cycle or if the new cycle is delayed due to toxicity newly encountered on the scheduled Day 1**, then the

new cycle will be started with a one-level dose reduction of the drug to which the toxicity was attributed.

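### Table 4 is mis-keyed: it labels 10 mg daily as the everolimus starting dose, so a patient on 5 mg who needs a reduction could be restarted at an unchanged 5 mg

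*Combined protocol and SAP*

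**What the plan says.** Section 5.7.1 has one reduction table per drug. Table 3 (lenalidomide) lists the dose at which toxicity occurred and, beside it, a lower dose. Table 4 (everolimus) has the same two kinds of column, both headed in mg per dose, but its left column holds level codes. The row "0 (starting dose" is paired with 10 mg daily, row -1 with 5 mg daily, and row -2 with 5 mg every other day.

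The everolimus starting dose is stated in four other places:

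- Synopsis, study design: "The proposed starting dose level 1 is 10mg of lenalidomide in combination with 5mg of everolimus".
- Section 5.6.2: "The planned starting dose of everolimus (RAD001) is an approved dose of 5 mg/day on a continuous basis".
- Table 1, row "Starting Dose 1": 5 mg everolimus.
- Section 5.1 narrative: starting lenalidomide is given "in combination with 10mg of everolimus (days 1 - 28) in a 28-day cycle".

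The first three agree on 5 mg. The fourth disagrees with Table 1 in its own section.

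Other instructions send the reader to a level. Section 5.7.2 says that after certain toxicities the "new cycle will be started with a one-level dose reduction of the drug to which the toxicity was attributed". Table 6 asks for everolimus to resume at a lower level after several grade 2 to 4 toxicities, and Table 7 asks for a one-level reduction after grade 3 pneumonitis.

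**The concern.** Table 4 is the only table of everolimus steps for individual patients, so the level-based instructions in section 5.7.2, Table 6 and Table 7 take their meaning from it. A user who takes the first-row label at face value will place a patient on the 5 mg starting dose in that row. One level down is then row -1, which is again 5 mg daily.

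The level codes make this slip easy. In Table 1, level 1 and level -1 both carry 5 mg everolimus, so a step from the starting level to level -1 also leaves everolimus unchanged there.

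At stake is the dosing of a patient who has just had a toxicity attributed to everolimus and who would resume the dose that preceded it. Such use is foreseeable: section 5.7.5 names grade 3 stomatitis as the principal dose-limiting toxicity of everolimus in Phase 1 trials, and section 5.7.3 directs reduction for non-hematologic toxicity at the drug most likely responsible.

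**Working it through.** The plan states no figure to reproduce, so the check compares the readings of Table 4.

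**Inputs.** Table 4 rows (section 5.7.1): 10 mg daily, 5 mg daily, 5 mg every other day. Starting dose: 5 mg daily (synopsis, Table 1, section 5.6.2). Cycle length: 28 days. The totals are for a full cycle; in cycle 1 everolimus begins on day 2 (section 5.6.2).

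**Everolimus per 28-day cycle** = mg per dose × number of doses.

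- 10 mg daily: 10 × 28 = 280 mg
- 5 mg daily: 5 × 28 = 140 mg
- 5 mg every other day: 5 × 14 = 70 mg

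**Readings of Table 4.**

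| Patient's dose | Reading | New dose | New/old total | Change |
|---|---|---|---|---|
| 5 mg daily | Match on dose taken, then one row down | 5 mg every other day | 70/140 = 0.5 | -50% |
| 5 mg daily | Enter at the starting-dose label, then one row down | 5 mg daily | 140/140 = 1.0 | none |
| 5 mg daily | Strictly by the headers, starting-dose row | 10 mg daily | 280/140 = 2.0 | doubled |
| 10 mg daily | Enter at the first row, then one row down | 5 mg daily | 140/280 = 0.5 | -50% |
| 10 mg daily | Strictly by the headers, first row | 10 mg daily | 280/280 = 1.0 | none |

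For a patient on 5 mg, the proper cut is reached only by setting the row labels aside and matching on the dose. Accepting the 10 mg start of the section 5.1 narrative does not rescue the headers, because the first row then sends 10 mg to 10 mg.

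**How far the label fits the design.** Of the seven dose levels in Table 1, level -2 uses "5mg every other day", levels -1, 1, 2, 3 and 4 use 5 mg, and level 5 uses 10 mg. The 10 mg label therefore fits 1 of 7 levels and misses 6.

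**What the intended step is.** Table 1 goes from 5 mg at level -1 to 5 mg every other day at level -2. Section 5.10 gives the same order for toxicity in patients on moderate CYP3A4 or PgP inhibitors. Both point to 5 mg every other day as the step below 5 mg daily.

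**The case against.** The strongest reply is that the intent can be recovered. The three doses are printed in descending order, there is only one step below 5 mg daily, and an experienced investigator would probably treat the table as a ladder. Table 1 has no level 0, so the 0 may be Table 4's own code for the full labelled everolimus dose of 10 mg. This stands as an account of what was probably meant. It does not explain why the row is called the starting dose when the dosing section starts at 5 mg.

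A reader might infer that the table instructs a dose increase. The headers taken alone do produce 10 mg, but the table's title, its right-hand header and the wording of section 5.7.2, Table 6 and Table 7 all call for a lower dose. The documents do not support an increase as a credible instruction; the plausible error is the unchanged dose.

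A reader might also count all 24 planned expansion patients (15 + 9) as exposed if the MTD contains 5 mg everolimus. The documents do not support that count. Only patients who need an everolimus reduction are sent to Table 4. For hematologic toxicity, section 5.7.3 reduces lenalidomide first, and Table 6 allows an everolimus reduction only when that has not been enough. For non-hematologic toxicity, only the more likely drug is reduced unless attribution is equal or unclear. Grade 4 non-hematologic toxicity and grade 4 thrombocytopenia lead to discontinuation of everolimus.

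Finally, a slip should be visible. Section 5.6.2 requires that "All dosages prescribed and dispensed to the patient and all dose changes during the study must be recorded", and section 9.3 has toxicity reviewed at weekly Phase I meetings. Both help to detect an error, mostly after the dose has been taken.

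**Conclusion.** Table 4 is wrong as labelled and should be corrected. Its first-row label contradicts the starting dose in the synopsis, Table 1 and section 5.6.2, and agrees only with the section 5.1 narrative, which itself conflicts with Table 1. The consequence for an affected patient is 140 mg per 28 days in place of 70 mg: no reduction where a halving is meant.

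This rests on two assumptions: that the start is 5 mg, as three of the four other statements say, and that the step meant below it is 5 mg every other day, as Table 1 and section 5.10 indicate. The number of patients on 5 mg who will need an everolimus reduction is not given, and the expansion dose is still to be determined in Table 1, so no count can be attached.

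The point concerns individual dosing only. Section 5.7.1 leaves cohort decisions to Table 1, and no estimate, test or sample size uses Table 4. A reader might see a further gap in the absence of a row for toxicity at 5 mg every other day. That is minor: section 5.11 and the stopping rules of Table 6 largely cover it, and Table 3 also ends without such a row.

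**What to change.** Key Table 4 by the dose being taken, in the format of Table 3:

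| Toxicity at | Reduce to |
|---|---|
| 10 mg daily | 5 mg daily |
| 5 mg daily | 5 mg every other day |

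Remove the level codes and the starting-dose label. In the same amendment, correct the section 5.1 narrative to a 5 mg everolimus start. A third row, discontinuing everolimus for toxicity at 5 mg every other day, is optional.

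The cost is a short protocol amendment covering one small table and one sentence, with no change to sample size, cohort rules or analysis.
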